11.2. Pharmacodynamic Parameters

Pharmacodynamic parameters will be calculated using actual timepoints using SAS[®] Version 9.3 or higher. Missing PD values will be treated as missing for PD parameter calculation.

The following PD parameters will be calculated using %baseline/actual MA and FA data, as appropriate, from the LTA assay for both the 5 μ M and 20 μ M ADP conditions.

Parameters following study drug infusion:	
APA _{max}	Maximal actual platelet aggregation
PA _{max}	Maximal percent of baseline platelet aggregation
TPA _{max}	Time to maximal actual platelet aggregation
TPA _{60%}	Time to 60% of baseline platelet aggregation, calculated as the first time point when %baseline platelet aggregation reaches 60% or above.
TPA _{80%}	Time to 80% of baseline platelet aggregation, calculated as the first time point when %baseline platelet aggregation reaches 80% or above
TPA _{90%}	Time to 90% of baseline platelet aggregation, calculated as the first time point when %baseline platelet aggregation reaches 90% or above

The following PD parameters will be calculated using %baseline/actual PRU data from the VerifyNow assay.

Parameters following study drug infusion:	
PRU _{max}	Maximal actual PRU
TPRU _{max}	Time to maximal actual PRU
TPRU ₂₀₀	Time to 200 or higher PRU, calculated as the first time point when the actual PRU reaches 200 or above
TPRU _{60%}	Time to 60% of baseline PRU, calculated as the first time point when %baseline PRU reaches 60% or above
TPRU _{80%}	Time to 80% of baseline PRU, calculated as the first time point when %baseline PRU reaches 80% or above
TPRU _{90%}	Time to 90% of baseline PRU, calculated as the first time point when %baseline PRU reaches 90% or above

The following PD parameters will be calculated using %baseline/actual PRI data from the VASP assay.

Parameters following study drug infusion:	
APRI _{max}	Maximal actual PRI
PRI _{max}	Maximal percent of baseline PRI
TPRI _{max}	Time to maximal actual PRI
TPRI _{60%}	Time to 60% of baseline PRI, calculated as the first time point when %baseline PRI reaches 60% or above
TPRI _{80%}	Time to 80% of baseline PRI, calculated as the first time point when %baseline PRI reaches 80% or above
TPRI _{90%}	Time to 90% of baseline PRI, calculated as the first time point when %baseline PRI reaches 90% or above

Additional PD parameters may be calculated, as necessary. Pharmacodynamic parameters will be listed by subject and summarized for each cohort using descriptive statistics (number of subjects, mean, SD, median, minimum, and maximum).

12. Changes in the Planned Analysis

For ECG measurements, QTcB interval will be calculated and a summary table for QTcF and QTcB values outside of pre-defined criteria will be produced.

13. Interim Analysis

There's no planned formal interim analysis for this study. Blinded safety data review for each dose cohort will be performed before dosing in the next cohort is allowed (Section 3.4.2.1 of the protocol).

Interim noncompartmental analyses of PK data and/or PK/PD modeling will be performed as needed.

14. Reference

Memo Re: PB2452-PT-CL-0001 Cohort 7 Dosing Regimen. To: [name], Principal Investigator, PPD Early Development Services; [name], Associate Director, Project Management, PPD Early Development. CC: [name], Project Manager, PPD Early Development. From: [name], Director, Clinical Operations. Date: July 3, 2018.

Memo Re: PB2452-PT-CL-0001 Cohort 8 Dosing Regimen. To: [name], Principal Investigator, PPD Early Development Services; [name], Associate Director, Project Management, PPD Early Development. CC: [name], Project Manager, PPD Early Development. From: [name], Director, Clinical Operations. Date: July 25, 2018.

Memo Re: PB2452-PT-CL-0001 Cohort9 and 10 Dosing Regimens. To: [name], Principal Investigator, PPD Early Development Services; [name], Associate Director, Project Management, PPD Early Development. CC: [name], Project Manager, PPD Early Development. From: [name], Sponsor Medical Consultant. Date: August 8, 2018.

15. Table of Contents: Tables, Listings and Figures

List of Tables	
Subject Disposition	
Table 14.1.1.	Subject Disposition
Demographics and Baseline Characteristics	
Table 14.1.2	Demographic and Baseline Characteristics (Safety Population)
Pharmacokinetics	
Table 14.2.1.1	Summary of Total Plasma PB2452 Concentrations (unit) (PK Population)
Table 14.2.1.2	Summary of Unbound Plasma PB2452 Concentrations (unit) (PK Population)
Table 14.2.1.3	Summary of Total Plasma Ticagrelor and AR-C124910XX Concentrations (unit) (PK Population)
Table 14.2.1.4	Summary of Unbound Plasma Ticagrelor and AR-C124910XX Concentrations (unit) (PK Population)

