4.1. General Data Presentation Rules

All data will be provided in individual by-subject listings.

Data from subjects excluded from an analysis population will be presented in the data listings but not included in the calculation of summary statistics.

Data from subjects receiving placebo will be pooled across cohorts for all presentations.

Unless otherwise noted, the following treatment groups will be used in summaries:

- 100 mg PB2452 (C1)
- 300 mg PB2452 (C2)
- 1000 mg PB2452 (C3)
- Placebo C1-C3
- 1000 mg PB2452 (C4)
- 3000 mg PB2452 (C5)
- 9000 mg PB2452 (C6)
- Placebo C4-C6
- 18000 mg PB2452 (C7)
- 18000 mg PB2452 (C8)
- 18000 mg PB2452 (C9)

- 18000 mg PB2452 (C10)
- Placebo C7-C10
- All Placebo (for safety summaries only)
- All PB2452 (for safety summaries only)
- All subjects

where 'C' means 'Cohort'.

Demographic data, baseline characteristics, adverse events (AEs), laboratory tests, vital signs, 12-lead electrocardiogram (ECG) measurements, and subject disposition will be summarized descriptively.

Unless otherwise noted, the summary of the continuous variables will include the number of subjects with non-missing data (n), mean, standard deviation (SD), median, minimum, and maximum. Categorical variables will be summarized descriptively by their counts and associated percentages. Percentages will be calculated using the number of subjects within a summary group as the denominator.

Minimum and maximum values will be presented as the same precision as the original value. Means and medians will be presented as 1 decimal place greater than the precision of the original value. Standard deviations will be presented as 2 decimal places greater than the precision of the original value. Percentages for summarizing categorical data will be presented with 1 decimal place. If the percentage value is less than 0.1, then "<0.1" will be displayed.

Unless specified otherwise, baseline for safety analyses is defined as the last non-missing measurement (including repeated and unscheduled measurements) prior to the first study drug administration; baseline for PD analyses is defined as the last non-missing measurement (including repeated and unscheduled measurements) prior to the first ticagrelor administration.

Listings will be sorted by treatment group and subject identifier.

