4.7. Handling of Missing Data

Subjects with missing data for some summary statistic will not be included in the calculation of that statistic but are eligible for inclusion in any other summary statistic for which they provide data. For the purpose of determining inclusion of AEs in treatment-emergent AE (TEAE) summary tables, incomplete or missing AE onset and end dates will be imputed as follows:

Incomplete or missing onset dates (where UK and UNK indicate unknown or missing day and month, respectively):

- UK-MMM-YYYY: If the month and year are different from the month and year of the dose of study drug, assume 01-MMM-YYYY. If the month and year are the same as the dose of study drug month and year, and the end date (after any imputation) is on or after the dose of study drug, then assume the date of the dose of study drug. If the month and year are the same as the dose of study drug month and year and the end date (after any imputation) is prior to the dose of study drug, then assume the end date for the onset date.
- DD-UNK-YYYY or UK-UNK-YYYY: If the year is different from the year of dose of study drug, assume DD-JAN-YYYY or 01-JAN-YYYY of the onset year, respectively. If the year is the same as the dose of study drug year, and the end date (after any imputation) is on or after the dose of study drug, then assume the date of the dose of study drug. If the year is the same as the dose of study drug, and the end date (after any imputation) is prior to the dose of study drug, then assume the end date for the onset date.
- Missing onset date: If the onset date is completely missing and the end date (after any imputation) is on or after the dose of study drug, then assume the date of the first dose of study drug. If the end date (after any imputation) is prior to the dose of study drug, then assume the end date for the onset date.

Incomplete or missing end dates (where UK and UNK indicate unknown or missing day and month respectively):

- UK-MMM-YYYY: Assume the last day of the month;
- DD-UNK-YYYY or UK-UNK-YYYY: Assume DD-DEC-YYYY or 31-DEC-YYYY, respectively;
- Missing end date: Assume 31-DEC-YYYY, where YYYY is the year of the dose of study drug.

An AE with missing onset time but with an onset date the same as the dosing date of study drug will be classified as treatment-emergent, unless the AE was reported pre-dose with the same or worse intensity or frequency.

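### SAP 11.2 has no rule for subjects who never reach a recovery threshold, so its time-to-threshold summaries by default describe attainers only

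*SAP*

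**What the plan says.** SAP 11.2 defines ten threshold times: three for LTA (60, 80 and 90% of baseline), four for VerifyNow (PRU 200, and 60, 80 and 90% of baseline) and three for VASP (60, 80 and 90% of baseline). The LTA 80% time is "calculated as the first time point when %baseline platelet aggregation reaches 80% or above", and the PRU 200 time is "calculated as the first time point when the actual PRU reaches 200 or above". The others have the same form. PD sampling ends 48 hours after the start of infusion (SAP 11.1).

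Three rules bear on a subject without such a time:

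- SAP 11.2: "Missing PD values will be treated as missing for PD parameter calculation".
- SAP 4.7: "Subjects with missing data for some summary statistic will not be included in the calculation of that statistic".
- SAP 4.1: "the summary of the continuous variables will include the number of subjects with non-missing data (n"), followed by the usual mean, SD, median, minimum and maximum.

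SAP 11.2 then has the PD parameters "summarized for each cohort using descriptive statistics (number of subjects, mean, SD, median, minimum, and maximum"). SAP 15 plans one parameter summary table per assay (Tables 14.2.6.1 to 14.2.6.3). No percentage attaining, censoring rule or time-to-event output is listed. The PD population (SAP 4.8) does not require recovery, so non-attainers belong to it.

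**The concern.** A time to recovery exists only for subjects who recover. If the others are left out, the summary answers how fast recovery was among those who had it. A reader of the table will probably take it as how fast recovery was in the group. The subjects removed are those with the worst outcome, so the omission always makes a group look quicker than it was.

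Comparisons between doses are exposed as well, because the share removed can differ from group to group. An active group has six subjects, or three if Cohort 9 or 10 stays at four subjects, so one or two exclusions can move the figures noticeably. LTA is the assay named in the primary effectiveness objective (SAP 2.1), and these tables will be read alongside it.

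**Working it through.** There is no figure in the plan to reproduce. The check follows a non-attainer through the rules and then shows the effect on assumed data.

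**1. Path through the rules.** Take a subject with every PD sample measured and every value below 80% of baseline.

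- The handling sentence in SAP 11.2 does not apply, since it concerns absent assay values and none is absent.
- The definition yields no time, because there is no first time point at or above 80%.
- With no value, the subject is outside n (SAP 4.1) and outside the statistic (SAP 4.7).

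SAP 4.7 does not name this case, but it is the only route the SAP offers. Protocol 3.6.4 covers concentrations only, and Protocol 3.6.3.3 plans descriptive statistics only.

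**2. Number of summaries affected, per group.** LTA: 3 thresholds × 2 measures (maximal and final extent) × 2 ADP concentrations = 12. VerifyNow: 4. VASP: 3. Total 12 + 4 + 3 = 19 at most.

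**3. Effect of losing the slowest subjects.** Six active subjects with assumed times 0.5, 1, 2, 3, 6 and 12 h. In each later row, one more of the slowest subjects fails to attain by 48 h.

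| Attain | Attainers-only mean (h) | Attainers-only median (h) | All-subject median |
|---|---|---|---|
| 6 of 6 | 24.5/6 = 4.08 | 2.5 | 2.5 h |
| 5 of 6 | 12.5/5 = 2.50 | 2.0 | 2.5 h |
| 4 of 6 | 6.5/4 = 1.625 | 1.5 | 2.5 h |
| 3 of 6 | 3.5/3 = 1.17 | 1.0 | between 2 h and >48 h |
| 2 of 6 | 1.5/2 = 0.75 | 0.75 | not reached |

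As fewer subjects recover, the attainers-only figures improve. The all-subject median stays put and then ceases to exist.

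**4. Reversal between groups (assumed times).**

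- Group A: 3 of 6 attain, all at 0.5 h. Attainers-only median 0.5 h.
- Group B: 6 of 6 attain, at 0.5, 0.5, 0.5, 1, 1 and 2 h. Median (0.5 + 1)/2 = 0.75 h; mean 5.5/6 = 0.92 h.

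A looks faster although half its subjects never recover. Because exactly half attain in A, its all-subject median depends on the convention. If the median is the earliest time by which at least half have attained, it is 0.5 h in both groups. If more than half must attain, it is not reached in A.

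With 2 of 6 attaining at 0.5 h, the attainers-only median is again 0.5 h. The third and fourth ordered times are both >48 h, so the all-subject median is not reached under either convention. With 1 of 3 attaining at 0.5 h, the attainers-only median is 0.5 h with no SD, and the all-subject median is not reached.

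**5. Chance that the case arises.** For an assumed attainment probability p and six independent subjects, P(at least one non-attainer) = 1 − p⁶.

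| p | P(at least one) |
|---|---|
| 0.95 | 0.265 |
| 0.90 | 0.469 |
| 0.75 | 0.822 |
| 0.50 | 0.984 |

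The documents do not give p. Protocol 1.3 describes 1000 mg, the Cohort 4 dose, as the expected minimally active dose, and pooled placebo groups are also summarized (SAP 4.1). Non-attainment is therefore foreseeable in some groups.

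**The case against.** The strongest reply is that the plan already shows who did not recover.

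- The number of subjects is printed with every summary, so a group of six with two attainers shows n = 2.
- For LTA the SAP plans "Maximal percent of baseline platelet aggregation", and a value below 80 means that the 80% time was not attained. VASP has the matching maximum.
- Parameters are listed by subject, and percent-of-baseline results for all three assays are listed and summarized at each time point (SAP 11.1).

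Most of this stands, and it limits the harm. Two gaps remain. First, n alone does not separate a subject who never reached the threshold from one who was not measured. Second, VerifyNow has only the maximal actual PRU. That shows who missed PRU 200, but not who missed 60, 80 or 90% of baseline; for those the reader must go to the per-time-point data.

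The second reply is that the times are secondary in weight. SAP 2.1 names LTA but makes no threshold time the primary endpoint, and no test, dose decision or sample size uses one. That is correct. A reader might infer that the primary effectiveness conclusion is biased; the documents do not support that.

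A reader might also infer that a programmer is free to enter 48 h for non-attainers, so that the table depends on an arbitrary choice. The SAP nowhere calls for that. Its rules point to exclusion, and the point rests on exclusion alone.

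Lastly, the examples are constructed, and late attainers at 12, 24 or 48 h would raise the attainers-only figures. True, but for subjects followed to 48 h the direction within a group is fixed, since every omitted time is longer than every included one.

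**Conclusion.** The gap is real and worth closing, with limited reach. As written, SAP 11.2 together with 4.1 and 4.7 produces threshold-time summaries that are conditional on attainment, and a group with fewer recoveries can show a shorter time. The effect is confined to these descriptive summaries. It would be too strong to say that non-attainment is hidden, because the other planned outputs show most of it.

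How large the distortion will be cannot be stated, because no attainment rate is given and every time in the examples is assumed. The conclusion also rests on the texts supplied. The SAP follows protocol amendment 5 of 03 August 2018, whereas the supplied protocol is dated 01 Feb 2018, so a rule in the later protocol cannot be excluded. The SAP's own silence is plain in the supplied text.

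**What to change.** In SAP 11.2 and Tables 14.2.6.1 to 14.2.6.3, for each threshold time:

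1. Report n/N (%) attaining, with N the PD-population subjects in the group. State separately how many non-attainers were sampled through 48 h and how many had an earlier last sample, so that an early leaver is not presented as an observed failure at 48 h.
2. List a non-attainer as later than the actual last sample time, distinct from not measured.
3. Replace the attainers-only median with an all-subject median that treats non-attainers as right-censored at the last actual sample (Kaplan-Meier). When everyone is followed to 48 h this equals the ordered-time median. State in advance the convention for exactly half attaining, and print 'not reached' where it applies.
4. Label any mean, SD and range 'attainers only' and place them next to n/N.

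The cost is a few SAP sentences and a few table rows, with no new data. Some medians will become 'not reached'.
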